11 LIST OF ABBREVIATIONS

Term	Definition
AE	adverse event
ALT	alanine aminotransferase
ANC	absolute neutrophil count
aPTT	activated partial thromboplastin time
AST	aspartate aminotransferase
AUC	area under the concentration-time curve
AUC(TAU)	area under the concentration-time curve in one dosing interval
BID, bid	bis in die, twice daily
BMI	body mass index
BMS	Bristol-Myers Squibb
BP	blood pressure
CBC	complete blood count
CI	confidence interval

Term	Definition
Cm	centimeter
Cmax, C _{MAX}	maximum observed concentration
Cmin, C _{MIN}	trough observed concentration
CNS	Central nervous system
CRF	Case Report Form, paper or electronic
CRNM	Clinically Relevant Non-Major
CSF	Cerebral spinal fluid
CVAD	Central Venous Access Device
CYP	cytochrome p-450
dL	deciliter
ECG	electrocardiogram
eCRF	Electronic Case Report Form
EDC	Electronic Data Capture
Eg	exempli gratia (for example)
FRP	Females of Reproductive Potential
FSH	follicle stimulating hormone
G	gram

[figure not shown]
Term	Definition
GCP	Good Clinical Practice
GGT	gamma-glutamyl transferase
GFR	glomerular filtration rate
H	hour
HBsAg	hepatitis B surface antigen
HCV	hepatitis C virus
HRT	hormone replacement therapy
ICH	International Conference on Harmonisation
Ie	id est (that is)
IEC	Independent Ethics Committee
IMP	investigational medicinal products
IND	Investigational New Drug Exemption
IRB	Institutional Review Board
IU	International Unit
IV	intravenous
Kg	kilogram
L	liter
LC	liquid chromatography

[figure not shown]
Term	Definition
LP	Lumbar puncture
Mg	milligram
Min	minute
mL	milliliter
NIMP	non-investigational medicinal products
NSAID	nonsteroidal anti-inflammatory drug
PD	pharmacodynamics
PK	pharmacokinetics
PO	per os (by mouth route of administration)
PT	prothrombin time
PTT	partial thromboplastin time
RBC	red blood cell
SAE	serious adverse event
SD	standard deviation

[figure not shown]

[figure not shown]
Term	Definition
[Redacted]	
WBC	white blood cell
[Redacted]	

[figure not shown]

[figure not shown]

APPENDIX 1 ULTRASOUND PROCEDURE

1 ULTRASOUND IMAGING PROTOCOL

1.1 General Imaging Concepts and Principles

Test protocols should be followed as closely as possible, but the examination should be representative of what is feasible in clinical practice. It is understood that the sequence of image acquisition and ability to obtain all suggested images will vary, depending on patient related factors such as age, clinical condition, ability to cooperate, etc. The extremity sonogram can be paired with other SOC procedures, such as lumbar puncture, as long as no additional sedation is required beyond what is used for the SOC procedure.

The Radiology Core Lab (RCL) will determine whether or not an exam is adequate for purposes of study inclusion.

- For all sites, the first patient recruited will receive a rapid turnaround feedback on the technique quality of its Ultrasound.
- If a chest radiograph was obtained, the most recent film, prior to performance of the ultrasound, should be submitted along with the ultrasound examination
- Sedation or anesthesia should not be used for research purposes only.
- A thrombus will be defined as a space occupying lesion seen within a vessel or associated with a Central Venous Access Device (CVAD). It may be hyper- or hypo- intense. It may be mobile or adherent to a vascular or cardiac structure. It may be occlusive (if no blood flow is seen on Doppler imaging in that segment of the vessel) or non-occlusive. The absence of color flow Doppler will typically profile the thrombus. Thrombus will be differentiated from a “fibrin sheath/line cast” which is a more linear structure, often mimicking the appearance of a CVAD, is not mobile, and is the known location of a prior CVAD.
- If the patient has a suspected thromboembolic event and the patient is not cooperating with the radiological interventions, sedation is recommended as per the institutional guidelines.
- The majority of the vascular sonogram should be performed using the highest frequency linear transducer possible, usually 7 - 15 MHz. However, the brachiocephalic veins and superior vena cava should be assessed via the suprasternal notch, using a microcase (small footprint)/vector transducer (generally 3 - 10 MHz).
- A bilateral examination should be performed, even if the subject is asymptomatic. When no clot is seen in association with the PICC/CVL, sonography of the opposite/contralateral (non-PICC/CVL) side can be less extensive. To clarify, the side with the PICC/CVL (ipsilateral) side should be assessed using the full protocol, to the extent that is possible. If no clot is seen on the ipsilateral side, the contralateral side may be evaluated in a targeted manner as follows:
For lower extremities: common femoral vein: long greyscale and long waveform views only.

For upper extremities: subclavian vein: long greyscale and long waveform views only.

However, if the site thinks there is a clot on the PICC/CVL (ipsilateral) side, a full examination on the contralateral side will be performed, following the full protocol, to the extent that this is possible.

- Label all venous images with laterality (RT/LT), the vein name (with abbreviation as listed below), and segment of the vein interrogated where appropriate (central, mid, peripheral), in that order.
- Real-time Grey scale imaging with transducer compression of the vein should always be used in areas where the vein is accessible to compression
 - Compression technique: The transducer is pressed gradually down to fully compress the vein. Arteries resist compression and are visibly pulsatile. In some areas, overlying strictures (bones, ligaments) may hamper full compression. Compression should be applied with the transducer at 1 cm intervals over the entire length of the vessel.
- Color Doppler imaging improves vessel conspicuity and may help to better definition of the thrombus. However, it is important to remember that improper selection of color Doppler parameters can obscure thrombi, particularly non occlusive thrombi.
 - Pulsed-Doppler waveforms are used to document cardiac phasicity, respiratory, and compression-induced flow changes.
 - Techniques to elicit changes in venous waveforms are termed augmentation maneuvers and include the Valsalva maneuver, sniffing, deep breathing, and ipsilateral venous compression by the linear transducer. Normal cardiac phasicity, respiratory variation and augmentation by direct venous compression are all markers of venous patency. Observation of asymmetry between right and left side waveforms implies the presence of a venous clot. However, observation of normal, symmetrical venous Doppler waveforms does not exclude the possibility of a non-occlusive thrombus.

1.2 Imaging Protocol: Upper Extremity Central Venous Access Device (CVAD) or Peripherally Inserted Central Venous Catheter (PICC)

- Most recent chest radiograph following line placement should be reviewed before ultrasound to determine the course of the CVAD or PICC and the location of the tip. During the ultrasound exam, the course of the catheter should be demonstrated in all involved vessels. Attempt should be made to visualize the tip of the catheter if it is located in the SVC or brachiocephalic, not if it is in the right atrium.

Use the “Upper Extremity Worksheet” as a study protocol guide.

The following veins should be scanned on both sides: **Internal Jugular (IJ), Subclavian (SCV), Brachiocephalic (innominate) veins (BC), Superior Vena cava (SVC), Axillary (Ax), Brachial (Brach), Basilic (Bas), and Cephalic veins (Ceph).**

- **Internal Jugular vein**
 - Use high frequency linear transducer.
 - Internal Jugular vein should be followed from the base of the skull to the junction with the subclavian/brachiocephalic veins.
 - Evaluate internal jugular vein using Grey scale imaging in the transverse plane, following its course from superior (distal) to inferior (proximal) compressing every 1 cm. Take representative images with and without compression at the superior, mid and inferior aspect of the vein.
 - Evaluate internal jugular vein using Grey scale imaging in the transverse plane, following its course from superior (distal) to inferior (proximal) compressing every 1 cm. Using dual

- screen, Take representative images without compression (left screen) and with compression (right screen) at the superior, mid and inferior aspect of the vein. Using the caliper/measuring tool, mark the margins of the non-compressed vein on the left image.
- Using dual screen, in the transverse plane, document grey scale (left screen) and color Doppler (right screen) views, without compression.
 - Obtain a longitudinal image of the internal jugular vein, with Grey scale imaging, assessing for intraluminal thrombus.
 - Obtain a longitudinal image of the internal jugular vein with color Doppler imaging, showing that the vessel fills uniformly, and excluding filling defect of fresh, hypoechoic thrombus.
 - Obtain pulsed Doppler wave form in the IJ vein the longitudinal plane, showing normal direction and phasicity/respiratory variation.
- **Subclavian vein**
 - Use high frequency linear transducer.
 - Evaluate the subclavian vein from lateral (peripheral) to medial (central) – from the junction with the axillary vein, to the junction with the internal jugular /brachiocephalic vein.
 - Evaluate entire subclavian vein in longitudinal plane using Grey scale imaging, evaluating for intraluminal thrombus, and take images that show the entire course of the vein.
 - Obtain color Doppler images of the subclavian vein in the longitudinal plane, showing that the vessel fills uniformly, and excluding filling defect of fresh, hypoechoic thrombus.
 - Obtain pulse Doppler waveforms of both the subclavian vein and the adjacent subclavian artery to show the normal relationship between the two vessels and distinguish the subclavian vein from venous collaterals that can form in setting of longstanding occlusion. Perform augmentation maneuvers (squeezing arm), to demonstrate appropriate response in the subclavian vein.
 - **Brachiocephalic/SVC**
 - From the suprasternal notch, use vector transducer/microcase if linear transducer does not allow visualization.
 - Obtain Grey scale coronal image showing the confluence of the subclavian and internal jugular veins into the brachiocephalic, evaluating for intraluminal thrombus. If possible obtain another Grey scale image angled down to see the more central portion of the brachiocephalic vein and SVC.
 - Obtain Color Doppler coronal image showing the confluence of the subclavian and internal jugular veins into the brachiocephalic. If possible obtain another Color Doppler image angled down to see the more central portion of the brachiocephalic vein and SVC. The goal is to show that the vessels fill in uniformly, excluding filling defect of thrombus.
 - If possible, obtain Pulse Doppler waveforms within the vessels showing normal direction and phasicity/respiratory variation (quiet breathing).
 - If possible, obtain Pulse Doppler waveforms within the vessels showing changes with augmentation maneuvers (Valsalva, sniffing, deep breathing).

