- To assess the effect of prophylactic apixaban versus no systemic anticoagulant during ~28 days of induction chemotherapy including asparaginase on single adjudicated endpoints of non-fatal DVT (including symptomatic and asymptomatic), PE, and CVST; and VTE-related-death.

- To assess the effect of prophylactic apixaban versus no systemic anticoagulant during ~28 days of induction chemotherapy including asparaginase on the composite endpoint of adjudicated major and clinically relevant non-major bleeding (CRNMB) events.

Study Design:

Figure -1: Study Design

Study Design:

Recruitment will start for children of ages 1 to < 18 years of age and weighing equal to or > 6 kg.

The current study is a randomized, open-label, multi-center clinical trial in which pediatric subjects will be randomized 1:1 to prophylactic apixaban for thromboembolism prevention versus no systemic anticoagulant prophylaxis during induction chemotherapy. Subjects randomized to apixaban will receive a prophylactic-dose of apixaban. While subjects ≥ 5 years may be administered either 2.5-mg, 0.5-mg tablets or oral solution apixaban, use of 2.5 mg or 0.5 mg tablets is encouraged. Subjects < 5 years and < 35 kg may be administered 0.5-mg tablets only.

Subjects will be administered apixaban twice daily by mouth or via a NGT or GT according to weight range as per below Table during approximately 28 days of induction chemotherapy including asparaginase.

Weight range	Dose
≥ 35 kg	2.5 mg twice daily
<35 to 25 kg	2 mg twice daily
<25 to 18 kg	1.5 mg twice daily
<18 to 10.5 kg	1 mg twice daily
<10.5 to 6 kg	0.5 mg twice daily

The previously communicated dosing for the body weight tier of 9 to < 12 kg has been redistributed into a 6 to < 10.5 kg weight tier and a 10.5 to < 18 kg weight tier.

Pediatric subjects randomized to apixaban should begin treatment following randomization (as long as conditions for apixaban administration are met). Study medication must be initiated prior to or within 12 hours of the first dose of asparaginase or by Day 4 \pm 3 of planned 3-4 drug systemic induction chemotherapy, whichever is first. Day 1 is the first day of planned 3-4 drug systemic induction ALL chemotherapy.

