8 STATISTICAL CONSIDERATIONS

8.1 Sample Size Determination

With a total of approximately 500 randomized subjects allocated with 1:1 ratio to the systemic thromboprophylaxis with apixaban or no systemic anticoagulant prophylaxis (control) group, there is more than 80% power to demonstrate superiority at a one-sided 0.025 level, assuming the true event rates of primary endpoint (composite of non-fatal asymptomatic and symptomatic DVT, pulmonary embolism (PE), and CVST; and VTE-related-death) are 17% and 8.5% in the control and the apixaban groups, respectively. Sample size estimation is based on Pearson's chi-square test.

Additionally, there is more than 80% power to demonstrate superiority at a one-sided 0.025 level, assuming the true event rates are 20% and 10% in the control and the apixaban groups, respectively with analyses that assume that 20% of the subjects will be excluded from the primary analysis due to either early dropout without end-of-treatment imaging evaluation or non-evaluable end-of-treatment imaging measurement in the calculation.

Randomization will be stratified by age groups as < 10 years or ≥ 10 to < 18 years, to reflect the major peaks of disease prevalence and risk stratification criteria for acute lymphoblastic leukemia (ALL) in children.^{40, 69, 70}

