- Color Doppler images in longitudinal plane, showing that the vessels fill in uniformly, and excluding filling defect of fresh, hypoechoic thrombus.
- Pulse Doppler waveforms showing normal direction and phasicity/respiratory variation.
- The tip of the catheter may be in the abdominal or intrahepatic IVC.

For all exams, the catheters should be imaged and labeled on longitudinal grey scale images of relevant vessels. If the tip is demonstrated, cine clip demonstrating the tip should be obtained.

Study is positive for deep venous thrombosis if there is a filling defect within any of the assessed vessels. It may be echogenic or hypoechoic (visible by absence of color flow Doppler), central or peripheral, depending on the chronicity of the thrombus. It may be occlusive (if no blood flow is seen on Doppler imaging in that segment of the vessel) or non-occlusive

If intraluminal thrombus is seen within a vessel, a clip demonstrating the thrombus should be obtained, longitudinal to the vessel. The length of the thrombus should also be measured in the longitudinal plane. The anterior to posterior (AP) and transverse (TV) dimensions should be measured in the transverse plane.

If a prominent valve is encountered which could be mistaken for thrombus, a cine clip should be obtained demonstrating its motion.

If there is venous stasis with rouleaux formation, causing increased echogenicity of the blood, a cine clip should be obtained showing motion in the vessel, and demonstrating that it is not a thrombus.

The thrombus will be categorized to:

- Occlusive thrombus: intraluminal filling defect is seen (thrombus), and color Doppler images do not demonstrate blood flow past this defect
- Non-occlusive thrombus: intraluminal filling defect is seen (thrombus), however color Doppler images demonstrate blood flow past this defect
- No thrombus: no intraluminal filling defect identified in the vessel

Presence of collateral vessels

Collateral vessels are present if there are unnamed smaller caliber circuitous veins adjacent to the vessel in question.

Report to accompany ultrasound images:

For each protocol ultrasound, the Center will send the local radiology report, will complete a worksheet that will detail compliance with the imaging protocol and complete a data form detailing interpretation and findings.

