4 ENDPOINTS

4.1 Primary Endpoints

Efficacy:

The primary efficacy endpoint is a composite of adjudicated non-fatal DVT (including asymptomatic and symptomatic), PE, and CVST and VTE-related-death objectively confirmed by independent adjudication. All components of the primary efficacy endpoint will be adjudicated by a blinded, independent adjudication committee.

Safety:

The primary safety endpoint will be adjudicated major bleeding which is defined as bleeding that satisfies one or more of the following criteria: (i) fatal bleeding; (ii) clinically overt bleeding associated with a decrease in hemoglobin of at least 20g/L (ie, 2g/dL) in a 24-hour period; (iii) bleeding that is retroperitoneal, pulmonary, intracranial, or otherwise involves the CNS; and/or (iv) bleeding that requires surgical intervention in an operating suite, including interventional radiology. Of note, the major bleeding will not be considered as part of the primary endpoint for the purpose of the European application, but will be assessed as part of the safety profile of apixaban.

Prophylactic transfusions without overt bleeding and without a decrease in hemoglobin of at least 20 g/L (i.e., 2 g/dL) in a 24-hour period are not considered bleeding events.

All bleeding events will be adjudicated by a blinded, independent adjudication committee as major bleeding, CRNM bleeding, or minor bleeding. These endpoints are consistent with those recommended by the International Society on Thrombosis and Haemostasis for pediatric clinical trials in venous thromboembolism.

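### Day 29 scans are acquired and first read by site staff who are not asked to be unaware of the arm, so differential detection of thrombus is possible and cheap to guard against

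*Protocol*

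**What the plan says.** **Design and masking.** The Protocol synopsis states: "The current study is a randomized, open-label, multi-center clinical trial in which pediatric subjects will be randomized 1:1 to prophylactic apixaban". The control is no systemic anticoagulant, without placebo. SAP 4.1 states the only masking: "All components of the primary efficacy endpoint will be adjudicated by a blinded, independent adjudication committee". Protocol 7.2 adds that the committee classifies from material supplied by investigators and refers to a charter, which is not among the documents.

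**Acquisition (Protocol Appendix 1, section 1.1).** The catheter side is to be scanned with the full protocol as far as feasible. The appendix accepts that the "ability to obtain all suggested images will vary, depending on patient related factors", and warns that badly chosen colour Doppler settings can hide clots, especially non-occlusive ones. If no clot is seen on the catheter side, the opposite side may be reduced to one vein in two views. Otherwise, "if the site thinks there is a clot on the PICC/CVL (ipsilateral) side, a full examination on the contralateral side will be performed".

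**Steps that follow the local impression.** A clip and measurements of a thrombus are taken if one is seen (Appendix 1, section 1.4). Extra Doppler interrogation on echocardiography is required if obstruction is suspected (Appendix 2, section 1.10). Protocol 5.4.1 accepts a catheter-side-only ultrasound if the procedure is difficult.

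**What travels with the images.** "For each protocol ultrasound, the Center will send the local radiology report", together with a compliance worksheet and a form giving interpretation and findings. Appendix 2, section 1.10 has the same for echocardiograms. The stated role of the two core laboratories is to decide whether an examination is adequate.

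**The concern.** Ultrasound and echocardiography results depend partly on how hard and how well the operator looks. In an open-label trial, the person holding the probe and the first reader may know whether the child is anticoagulated. The timing rule can also be a cue: Protocol 5.4.1 dates imaging from the end of study medication in the apixaban arm and from the Day 29 visit in the control arm.

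If staff look less hard in children known to be on apixaban, fewer clots are recorded in that arm. The relative risk then moves in apixaban's favour and the false-positive rate rises above its nominal level. Adjudicating stored images blind protects the classification of what was recorded, but cannot supply views that were not taken. The sensitivity analyses in SAP 7.5.1.1 deal with missing or non-evaluable imaging and with protocol deviations. None deals with unequal detection among scans accepted as adequate.

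**Working it through.** **Step 1. Reproduce the plan's power.** Protocol 8.1 gives the inputs: "With a total of approximately 500 randomized subjects allocated with 1:1 ratio"; event rates that "are 17% and 8.5% in the control and the apixaban groups, respectively"; and "there is more than 80% power to demonstrate superiority at a one-sided 0.025 level". The stated test is Pearson's chi-square. With p̄ the mean of the two rates,

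power = Φ{ [p1 − p2 − 1.96·√(2p̄(1−p̄)/n)] / √([p1(1−p1) + p2(1−p2)]/n) }.

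- 17% vs 8.5%, n = 250 per arm: (0.085 − 1.96 × 0.02983)/0.02959 = 0.897, so power is 81.5% (82.1% by exact binomial enumeration).
- 20% vs 10%, n = 200 per arm after the 20% exclusion: (0.100 − 1.96 × 0.03571)/0.03536 = 0.849, so power is 80.2% (81.1% exact).

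Both stated claims of more than 80% hold. The same formula can therefore be used below. It is unstratified, as the sizing was; the primary test is stratified by age.

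**Step 2. Add unequal detection.** Let f be the share of primary events found by scan, and r the detection of those events in the apixaban arm relative to control. Events found clinically are taken as equally detected. Then

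observed apixaban rate = p × (1 − f + f·r).

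Neither f nor r is in the documents; both are assumptions. With no true effect, p = 17% in both arms and n = 250 per arm, the chance of a one-sided significant result in favour of apixaban is:

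| f | r = 1.00 | r = 0.95 | r = 0.90 | r = 0.80 |
|---|---|---|---|---|
| 50% | 2.5% | 3.3% | 4.4% | 7.4% |
| 75% | 2.5% | 3.8% | 5.8% | 11.9% |
| 90% | 2.5% | 4.2% | 6.7% | 15.5% |

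Worked cell, f = 50% and r = 0.90: the observed apixaban rate is 0.17 × 0.95 = 16.15%, so the expected relative risk is 0.95. Then (0.0085 − 1.96 × 0.03326)/0.03326 = −1.70, which gives 4.4%. For f = 90% and r = 0.90 the rate is 0.17 × 0.91 = 15.47%, the relative risk is 0.91 and the error is 6.7%. Exact enumeration gives 4.4% and 6.7% as well.

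**Step 3. Effect on the estimate.** If the observed relative risk were 0.50, the true value would be 0.50/(1 − f + f·r). At r = 0.90 that is 0.53 to 0.55 for f from 50% to 90%. At r = 0.80 it is 0.56 to 0.61.

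**Step 4. The contralateral rule alone.** The endpoint is yes or no per child. A confirmed catheter-side clot already makes the child an event, so the extra contralateral views matter only if the catheter-side suspicion is not confirmed (assumed 2% to 20% of the arm) and a clot lies outside the reduced contralateral view (assumed 0.5% to 5% of those). That is 250 × 0.02 × 0.005 = 0.03 children up to 250 × 0.20 × 0.05 = 2.5 children per arm. This route is minor.

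**The case against.** Several points on the other side stand.

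- **Catheter side.** It gets the full protocol in every child regardless of the local reading. A reader might infer from the contralateral rule that the site decides how thoroughly each child is scanned; step 4 shows that this rule can rarely change a child's status.
- **Share of events.** A reader might assume that the scans supply most primary events. The documents give no split by detection route. A share of 75% can be backed out: 0.8 × 20% + 0.2 × s = 17% gives s = 5%, and (20% − 5%)/20% = 75%. This works only if the two power scenarios describe one population, which the plan does not say. Nor are these scans the only source of asymptomatic DVT: Appendix 3 also covers clots found incidentally on other imaging.
- **Variation in images.** Appendix 1 ties this to the patient's age, condition and cooperation, not to the operator. The support for operator dependence is the warning on Doppler settings.
- **Central safeguards.** The committee is stated to be blinded. That the site sends its report does not show that central readers see it first; the charter may settle the order. The compliance worksheets and adequacy checks would let gross differences in scanning effort be compared by arm.

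What remains is not answered by these points: no masking is stated at acquisition or first reading, no central re-reading of scans that the site calls negative is stated, and no later step restores a view that was not taken.

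**Conclusion.** The point holds as a gap in protection against detection bias, not as evidence that bias occurred. The imaging rules are the same in both arms; harm requires that knowledge of the arm changes how staff scan or read. Under the stated assumptions, a 10% relative deficit in detection in the apixaban arm would raise the one-sided type I error from 2.5% to about 4.4% to 6.7%, and would make an observed relative risk of 0.50 correspond to a true one of about 0.53 to 0.55. With equal detection nothing changes. A deficit in the control arm would work against apixaban instead. The stronger reading, that the trial's false-positive rate is inflated or that adjudication is not independent, is not supported: no figure for unequal detection is given, and the committee's procedure lies in a charter that the documents do not include. The change is worth making because it is cheap and acts where the blinded committee cannot.

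**What to change.** Add to Appendices 1 and 2:

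1. The scan request carries the study number and not the treatment arm. The sonographer, echocardiographer and local reader are not told the arm, where feasible.
2. Where scans are read centrally or adjudicated, the reading is recorded before the local report and interpretation form are seen, and treatment information is removed from the imaging package. Vendor de-identification is described only for CVST, arterial and bloodstream-infection dossiers (Appendices 5, 6 and 7). It should be extended to Day 29 scans, with removal of treatment information, unless the charter already provides this.

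The cost is wording in the appendices, the imaging manual and the request form, plus a small handling burden for the packages. No extra visit, scan or staff is needed. The downside is that bedside masking will be imperfect, since families and ward staff know the arm.
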